Note: Seasonal influenza vaccines are usually inactivated influenza vaccines and are allowed; however, intranasal influenza vaccines (e.g., FluMist®) are attenuated live vaccines and are not allowed.

History of immunodeficiency, including positive for human immunodeficiency virus (HIV) or other acquired or congenital immunodeficiency diseases, or history of organ transplantation;

Active hepatitis B virus (HBV) infection [positive for hepatitis B surface antigen (HBsAg) or hepatitis B core antibody (HBcAb) and HBV DNA >500 IU/mL], hepatitis C virus (HCV) infection [positive for HCV antibody and HCV RNA by polymerase chain reaction (PCR) above the upper limit of normal], or positive for anti-human immunodeficiency virus antibody (Anti-HIV);

Serious chronic or active infections (including tuberculosis infection) requiring systemic antibacterial, antifungal, or antiviral treatment within 4 weeks prior to the start of the study treatment;

Note: Patients with viral hepatitis are allowed to receive antiviral treatment.

Severe cardiovascular diseases, including but not limited to:

History of acute coronary syndrome or coronary artery angioplasty/stent placement/bypass surgery within the past 6 months;

New York Heart Association (NYHA) (see Appendix 4) class II-IV congestive heart failure (CHF), or history of NYHA class III or IV CHF.

Active psychiatric disorders (schizophrenia, severe depressive disorder, bipolar disorder, etc.);

Known allergy or intolerance to the active ingredient, excipients, or other iron supplementation products of the investigational drug;

Participated in other interventional clinical studies within 4 weeks prior to the start of the study treatment (calculated from the first day after the last dose of the previous study, except for those who did not use any investigational drugs or medical devices);

Any other condition that the investigator deems unsuitable for the patient to participate in this study.

Criteria for Suspension of Clinical Trials:

The trial will be suspended until the cause is confirmed and the safety review committee (SRC) composed of the sponsor and investigators, etc. discusses and determines that the trial can be restarted, under the following circumstances:

Any death of a subject not due to disease progression within 21 days (inclusive) after injection of CNSI-Fe;

Multiple subjects discontinue study drug treatment for reasons other than disease

progression;

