The incidence and severity of adverse drug reactions indicate that the risks of the study drug regimen outweigh the benefits;

The quality of data recording is too poor, inaccurate and/or incomplete.

Withdrawal Criteria:

Withdrawal Decided by Investigators: Withdrawal decided by investigators refers to the situation where a selected participant is deemed unsuitable to continue the study during the research process, and the investigator decides to withdraw the participant from the study. This includes, but is not limited to, the following situations:

The participant has seriously deviated from or violated the protocol, and this has affected the evaluation of the drug's efficacy or safety, so the participant must be withdrawn from the study;

The investigator believes that the participant should be withdrawn from the study for other reasons.

Withdrawal Decided by Participants: According to the Good Clinical Practice (GCP) for Pharmaceutical Trials and the International Council for Harmonisation of Technical Requirements for Pharmaceuticals for Human Use (ICH) Guideline E6, all participants have the right to withdraw from the study at any time during the trial, or if the participant no longer accepts medication and testing but does not explicitly request withdrawal, this is also considered "withdrawal" (or "dropout"). The reasons for withdrawal should be understood as much as possible and recorded, such as:

unable to tolerate certain adverse events; unable to continue the clinical study due to other reasons; or lost to follow-up without explanation, etc.

Handling of Withdrawn Cases

Investigators must record the reason for participant withdrawal in the electronic case report form (eCRF), and try to contact the participant as much as possible to complete the assessments that can be done. Regardless of the reason, the eCRF of the withdrawn case should be retained. For withdrawn cases where adverse events exist at the time of study termination, the follow-up requirements for the adverse events are described in Section 8.6.

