This study will enroll patients with advanced solid tumors and use the traditional "3+3 method" for dose escalation. The dose escalation principle is: in any dose cohort, 3 subjects will be enrolled first. If none of the first 3 subjects experience DLT during the DLT evaluation period, the next dose cohort can be entered. If ≥ 2 of the first 3 subjects experience DLT during the DLT evaluation period, dose escalation will be stopped (for the 30 mg cohort, if 2 DLTs occur, the sponsor and investigator will jointly decide whether to reduce the dose and continue exploration). If 1 of the first 3 subjects experiences DLT during the DLT evaluation period, an additional 3 subjects will be enrolled in that dose cohort, and if ≤ 1 of the 6 subjects in that dose cohort experience DLT during the DLT evaluation period, the next dose cohort can be entered; if ≥ 2 of the 6 subjects in that dose cohort experience DLT during the DLT

evaluation period, dose escalation will be stopped. The dose prior to the dose at which $\geq 2/3$ or $\geq 2/6$ subjects experience DLT during the DLT evaluation period will be determined as the MTD (if only 3 subjects are enrolled in a cohort, an additional 3 subjects will need to be enrolled).

The “3+3” dose escalation principle

The number of subjects who experienced a dose-limiting toxicity (DLT) within a particular dose cohort	dose escalation principle
0/3	no DLT is observed in the 3 newly enrolled subjects
0/3	no DLT is observed in the 3 newly enrolled subjects
$\geq 2/3$	Dose escalation should be stopped, and that dose will be considered the Maximum Administered Dose (MAD). If the previous lower dose was only administered to 3 subjects, then 3 more subjects need to be enrolled
1/3	
If the 3 newly enrolled subjects in the dose group do not experience a DLT (Dose-Limiting Toxicity), then the study will proceed to the next dose group.
 
 ● ● If ≥ 1 of the 3 newly enrolled subjects in the dose group experience a DLT, then dose escalation will be stopped, and that dose level will be considered the MAD (Maximum Administered Dose). The previous dose level will be considered the MTD (Maximum Tolerated Dose) (if the dose group only had 3 subjects, then an additional 3 subjects will need to be enrolled).

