The DLT (Dose-Limiting Toxicity) evaluation period is in the first cycle, i.e., within 21 days after the first dose. This stage is tentatively set with 3 dose groups (calculated as Fe^{2+} , 30 mg, 60 mg, 90 mg). If ≥ 2 subjects in the 90 mg group observe DLT, the dose will be reduced to 75 mg for safety and tolerability observation; if the dose is increased to 90 mg and MTD (Maximum Tolerated Dose) is still not reached, the SRC

(Safety Review Committee) will discuss continuing to escalate the dose to 120 mg, 150 mg, or even higher (if MTD is still not reached at 120 mg, the SRC will discuss whether to stop dose escalation or directly proceed to 150 mg or even higher doses).

After 3-6 subjects in each dose group have completed the DLT evaluation, the SRC will evaluate the overall safety of each dose group based on the data obtained and determine whether to continue escalating to the next dose group or to determine the recommended dose for subsequent clinical development.

Enrollment Interval: To fully protect the safety of the subjects, during the dose escalation process, the first subject in each dose group must be dosed at least 3 days after the first dose, and the remaining subjects in that dose group can then start the first dose. The interval for subsequent subjects in the same dose group can be controlled at the discretion of the investigator. The last subject in each dose group must complete the DLT evaluation, and the safety and tolerability must be reviewed by the SRC before the first subject in the next dose group can receive the first dose.

Subject Replacement: During the DLT evaluation period, if a subject is unable to be evaluated for DLT (e.g., the subject's dose of the study drug did not reach at least 80% of the protocol-specified dose, or the subject discontinued study treatment before completing the DLT evaluation period for reasons other than DLT), additional subjects will need to be enrolled to make up the corresponding number in that dose

group.

DLT Definition: This study will grade toxicities according to NCI CTCAE v5.0. DLT refers to the following toxicity reactions that are considered by the investigator and/or the sponsor to be definitely or possibly related to the study drug CNSI-Fe, occurring within the first cycle (i.e., within 21 days after the first dose):

Hematological toxicity:

- (1) Any grade 4 hematological toxicity;

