- (2) Any grade 3 hematological toxicity that persists for >7 days after best supportive care, or grade 3 thrombocytopenia with bleeding tendency or requiring platelet transfusion;
- (3) Grade 3 neutropenia with fever, defined as: ANC<1×10⁹/L and a single temperature >38.3°C or sustained temperature ≥38°C for >1 hour.

Non-hematological toxicity:

- (1) Grade 3 cardiac toxicity that persists for >3 days after best supportive care, or grade 4 cardiac toxicity;
- (2) Grade 3 hepatic toxicity (for subjects with liver or bone metastases, and baseline grade 2 liver transaminases, ALT, AST or ALP >10×ULN) that persists for >3 days after best supportive care, or grade 4 hepatic toxicity;
- (3) Any grade 3 non-hematological toxicity (excluding laboratory tests) that persists

for >7 days after best supportive care, except for grade 3 nausea, vomiting or diarrhea;

(4) Any grade 4 non-hematological toxicity (excluding laboratory tests);

(5) Any grade 3 or 4 non-hematological laboratory abnormality, if:

It requires medical intervention;

Or leads to hospitalization;

Or persists at grade 3 or above for ≥ 7 days after drug discontinuation.

Others:

(1) Any grade 5 toxicity;

(2) Other grade toxicities that the investigator and sponsor agree require early termination of CNSI-Fe treatment.

This study will not only observe the safety and tolerability of CNSI-Fe, but also preliminarily evaluate the efficacy of CNSI-Fe in patients with advanced solid tumors.

The investigators will evaluate the efficacy of CNSI-Fe based on the results of imaging examinations [computed tomography (CT), positron emission tomography (PET)/CT, or magnetic resonance imaging (MRI)], referring to the revised RECIST v1.1 and RECIST v1.1.

Contrast-enhanced CT or contrast-enhanced MRI is the preferred imaging method for evaluating tumor response. If the subject is known to be allergic to the contrast agent, if possible, obtain a contrast agent evaluation using local preventive standards, or use

alternative methods. In cases where contrast agents are strictly contraindicated, non-contrast scans should be performed. If the subject is contraindicated for contrast-enhanced CT scans, a non-contrast chest CT scan and contrast-enhanced abdominal and pelvic MRI scan can be performed.

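### The DLT exception for nausea, vomiting and diarrhea carries no condition, so it acts only on persistent events, including those still at grade 3

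*Combined protocol and SAP*

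**What the plan says.** The DLT Definition in the protocol synopsis covers toxicities definitely or possibly related to CNSI-Fe within 21 days of the first dose. Under Non-hematological toxicity, limb (3) takes any grade 3 clinical (non-laboratory) toxicity that persists "for >7 days after best supportive care, except for grade 3 nausea, vomiting or diarrhea". The exception states no duration, response to treatment or other condition.

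The other routes to a DLT that matter here are:

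- Limb (4): grade 4 clinical toxicity.
- Limb (5): grade 3 or 4 laboratory abnormalities that need intervention, lead to hospitalization, or last. For the last of these the wording is "persists at grade 3 or above", for at least 7 days after stopping the drug.
- Others (1): any grade 5 toxicity.
- Others (2): "Other grade toxicities that the investigator and sponsor agree require early termination of CNSI-Fe treatment".

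Under Dose Escalation, the 3+3 rule reads: "If none of the first 3 subjects experience DLT during the DLT evaluation period, the next dose cohort can be entered". One DLT in three leads to three more subjects, and two or more in three or in six stop escalation. DLT incidence is listed among the primary endpoints.

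**The concern.** An exception for these three symptoms normally spares events that antiemetics or antidiarrheals bring under control. Limb (3) already does that through its 7-day requirement. The exception therefore reaches the opposite group, the events that supportive care did not resolve in a week.

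The DLT count sets escalation, the MTD and, at 90 mg, the step down to 75 mg. If refractory grade 3 vomiting or diarrhea is not scored, the count can understate intolerance at a dose.

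A subject may also leave before Day 21 because of such an event; Withdrawal Decided by Participants lists "unable to tolerate certain adverse events" as a reason. Unless Others (2) is invoked, that subject fits the replacement rule, under which "the subject discontinued study treatment before completing the DLT evaluation period for reasons other than DLT" makes a subject non-evaluable, and another subject takes the place.

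**Working it through.** The plan states no figure on this point. The check is mainly one of logic.

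**Step 1. What the exception changes in limb (3), for a drug-related grade 3 clinical event**

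| Symptom | Persists >7 days after supportive care | Without exception | With exception |
|---|---|---|---|
| Other | No | Not DLT | Not DLT |
| Other | Yes | DLT | DLT |
| Nausea, vomiting, diarrhea | No | Not DLT | Not DLT |
| Nausea, vomiting, diarrhea | Yes | DLT | **Not DLT** |

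Only the last row changes.

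**Step 2. What persisting means.** Limb (3) does not say whether the event must stay at grade 3 or merely be unresolved. Limb (5) does say so ("persists at grade 3 or above").

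- If limb (3) means still at grade 3, every exempted event is a refractory grade 3 event.
- If it means unresolved, the exempted group also holds events that fell to grade 1 or 2 and lingered, where an exemption is sensible.

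Events still at grade 3 are exempt on either reading.

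**Step 3. Effect on the 3+3 score.** First three subjects, events in different subjects, no other DLT route applying:

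| Among the first 3 | Score as written | Score if counted |
|---|---|---|
| 1 exempted event | 0/3, may escalate | 1/3, enroll 3 more |
| 1 exempted event and 1 other DLT | 1/3, enroll 3 more | 2/3, stop |
| 2 exempted events | 0/3, may escalate | 2/3, stop |

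**Step 4. Illustration under assumed rates.** Let r be the share of subjects with a drug-related event of this kind still at grade 3 after more than 7 days of supportive care and no other DLT. Let d be the rate of other DLTs. Both are assumptions. With p = d + r and q = 1 − p, the rule stops at a dose with probability 1 − (q³ + 3pq⁵). As written, p = d.

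For example, with d = 10% and r = 5%, p = 0.15 and q = 0.85, so 1 − (0.6141 + 0.1997) = 0.1862. As written, p = 0.10 gives 1 − (0.7290 + 0.1771) = 0.0939.

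| r (assumed) | At least 1 of 3 affected: 1 − (1 − r)³ | At least 2 of 3: 3r²(1 − r) + r³ | Stop probability, d = 0 (as written: 0) | Stop probability, d = 10% (as written: 0.0939) |
|---|---|---|---|---|
| 1% | 3.0% | 0.03% | 0.0012 | 0.1108 (+1.7 points) |
| 2% | 5.9% | 0.12% | 0.0046 | 0.1285 (+3.5 points) |
| 5% | 14.3% | 0.73% | 0.0266 | 0.1862 (+9.2 points) |

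If the two kinds of event are taken as independent instead of non-overlapping, the 5% and 10% case gives an escalation probability of 0.824 in place of 1 − 0.1862 = 0.814. SRC holds, suspension and Others (2) are not modelled and would shrink all these differences.

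**The case against.** The strongest reply is that the plan has other ways to catch such a case.

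- Others (2) is written for toxicities that the numbered limbs miss. Refractory grade 3 vomiting judged to rule out the second injection could be called under it.
- Limb (4) takes grade 4 events. Limb (5) takes laboratory consequences that need intervention, with chemistry on Days 7, 14 and 21.
- A 0/3 score permits escalation but does not force it. Under Enrollment Interval, "the safety and tolerability must be reviewed by the SRC before the first subject in the next dose group can receive the first dose".
- The suspension criteria include risks judged to outweigh benefits, and "Multiple subjects discontinue study drug treatment for reasons other than disease" progression.
- All adverse events are reported and tabulated by dose group.
- Replacement after a non-DLT withdrawal applies to any adverse event and is not peculiar to this clause.

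Much of this stands. A reader might infer that refractory grade 3 vomiting or diarrhea can never be a DLT, or that the plan will escalate over it. The documents support neither. What remains is that these routes need the event to worsen, to have a separate qualifying consequence, or to be judged to require action. SRC review and suspension act on the conduct of the trial; they do not change the DLT count or the MTD derived from it.

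It is also fair to say that nothing in the documents shows these events occur with CNSI-Fe, which in cycle 1 is tentatively a single intratumoral injection. The figures under assumed rates are therefore not evidence of a material effect. They would also overstate the effect of the change proposed below if r were taken to include lingering grade 1 or 2 events.

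**Conclusion.** The point holds as a specific flaw in the wording of limb (3), and the sponsor should correct it. The exception can only remove persistent drug-related events, including those still at grade 3, and the stated rule can then score 0/3 where 1/3 or 2/3 is warranted. That follows from the text and needs no assumed rate.

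The size is unknown. If such events are rare it is small: with no other DLTs, counting them raises the stop probability at a dose by 0.1 to 2.7 percentage points for assumed rates of 1% to 5%. The larger increase of 9.2 points needs two assumptions together, 5% such events and 10% other DLTs.

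A reader might also infer that every exempted event should count. The documents do not support that, because the bare use of persists may cover events that have dropped to a low grade.

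Confidence is medium. The text available for review ends in the notes to the trial flow diagram (Table 1-1), so a qualifier in a DLT section of the protocol body cannot be excluded. If one exists, the synopsis still needs to match it.

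**What to change.** Leave the rest of limb (3) unchanged and qualify only the exception, for example: *except for grade 3 nausea, vomiting or diarrhea that falls to grade 2 or lower within 7 days of best supportive care*. Align any DLT section in the protocol body.

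Two broader edits are less suitable. Deleting the exception would, if persisting means merely unresolved, also count low-grade symptoms that linger. Rewording the whole limb to require persistence at grade 3 would, on that same reading, stop counting other grade 3 toxicities that fall to grade 1 or 2 and linger. It would also depart from the unqualified wording in hematological limb (2) and non-hematological limbs (1) and (2).

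The cost is one clause. A few more events may count as DLTs, so a cohort may expand to six subjects or escalation may stop earlier.

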Study Design: This is an open-label, dose-escalation Phase I clinical study conducted in patients with advanced solid tumors, aiming to evaluate the safety, tolerability, PK/PD characteristics, and preliminary efficacy of CNSI-Fe intratumoral injection in patients with advanced solid tumors.

Study Period: The study includes a screening period, a treatment period (including DLT evaluation period), and a follow-up period.

Screening Period: -28 to -1 days, to confirm that the subjects meet the inclusion criteria and do not meet the exclusion criteria.

Treatment Period (including DLT Evaluation Period): The DLT evaluation period is the first treatment cycle (duration: 21 days). During the DLT evaluation period, all subjects will receive CNSI-Fe intratumoral injection according to the protocol plan (preferentially selecting 1 suitable lesion for injection, tentatively with 1 injection on Day 1; if the corresponding dose of the investigational drug cannot be completed in 1 lesion, other lesions can be injected simultaneously; the dosing regimen may be adjusted by the sponsor and investigator based on the PK characteristics of this study). Safety assessments will be performed on Day 7, Day 14, and Day 21 after the first dose to evaluate DLT.

After the DLT evaluation is completed, subjects who do not experience unacceptable toxicity, if the investigator judges that the benefit of continued treatment outweighs

the risk, will enter the maintenance treatment period. In the maintenance treatment period, subjects will continue to receive one more dose of the investigational drug according to the DLT evaluation period dosing regimen (injection into the same lesion as the DLT evaluation period, tentatively with 1 injection on Day 1, the dosing regimen may be adjusted by the sponsor and investigator based on the PK characteristics of this study), and safety assessments will be performed on Day 7, Day 14, and Day 21 after dosing. Samples will be collected at the predetermined timepoints according to the study flow chart.

Follow-up Period: Safety follow-up until 28 days after the last dose.

Dose Escalation

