The baseline imaging evaluation will be performed within 28 days prior to the first study treatment (if the subject has undergone imaging examinations at the study site during the routine clinical care process prior to signing the ICF, and the examination site and method meet the protocol requirements, and the examination time is within 28 days prior to the first study treatment, the corresponding examination results may be used for this trial's screening after the investigator's consent).

All subjects will undergo tumor assessment once every 3-4 weeks during the study treatment period, and once every 7-8 weeks for those who enter the maintenance treatment period (the investigator may decide whether to perform additional imaging examinations for special changes in the disease condition, and the first tumor assessment must be performed at 3-4 weeks).

Subjects who achieve a complete response (CR) or partial response (PR) in the first assessment will require confirmation at least 4 weeks later.

The baseline tumor evaluation must include the chest, abdomen, pelvis, and head (to

exclude brain metastases), as well as other suspected tumor sites. Subsequent evaluations should re-evaluate all measurable and evaluable lesions found at baseline, including the chest, abdomen, pelvis, and other suspected tumor sites.

The imaging examination methods used for efficacy evaluation of subjects during the study period must be consistent with the baseline imaging evaluation methods.

Investigational medicinal products

The CNSI-Fe involved in this study is composed of a ferrous iron adsorbed carbon nanoparticle, which are prepared and used on-site. The drug information is as follows:

Drug Name	Dosage Form	Specification	Storage Conditions	Shelf Life
CNSI-Fe(II)	Injection	2 mL: 100 mg	Store at 2-8°C	24 months
Ferrous Sulfate for Injection Lyophilized	Powder for Injection	30 mg/vial (as ferrous)	Store at 2-8°C, protected from light	24 months

The carbon nanoparticle suspension injection and the ferrous sulfate injection are both provided by the applicant.

Packaging and labeling: The nano carbon suspension injection and the ferrous sulfate injection are labeled by the applicant according to the "Good Manufacturing Practice for Drugs (Revised in 2010)" (NMPA, 2011) and the "Good Clinical Practice for Drugs" (NMPA, 2020), and are marked as for clinical trial use only.

dosage regimen

Dose Escalation Phase (DLT Phase)

Dosing

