Safety Analysis: For the primary estimand, the number of subjects, incidence, and number of events of each type of adverse event will be summarized by dose group.

Numerical laboratory data at each visit will be described using mean, SD, median, extremes, and changes from baseline, and categorized as normal, clinically insignificant abnormal, or clinically significant abnormal, with the incidence of clinically significant abnormalities tabulated. The same approach will be used for ECG. Vital signs will be described using mean \pm SD.

For the secondary estimand, the incidence of DLTs will be summarized by dose

group.

PK Analysis: The primary PK endpoints for CNSI-Fe intratumoral injection will include the iron ion concentration in serum. PK analyses will provide descriptive statistics of the relevant measurements and concentration-time profiles. For the first dose of CNSI-Fe, AUC, Cmax, Tmax, and other parameters may be calculated. Descriptive statistics will be provided for these parameters, and informal testing of AUC may be performed to explore the relationship with dose.

Efficacy Analysis: Based on best lesion response, ORR, DCR, and their two-sided 95% confidence intervals (Clopper-Pearson method) will be statistically described.

PD Analysis: Descriptive statistics will be provided for the PD endpoint levels before and after dosing, as well as the changes (absolute or percent) from baseline. Corresponding time course profiles will be generated. Comparisons of the PD endpoint levels and changes from baseline at each timepoint will be performed, with normality testing and using paired t-tests or Wilcoxon signed-rank tests as appropriate.

Research on time:

After this study has been reviewed and approved by the Ethics Committee (EC), it

will continue until the expected sample size is reached, based on the actual situation.

The study is expected to end 28 days after the last participant receives a maximum of two doses. For participants who still achieve CR (complete response) or PR (partial response) at the end of the study, if the investigator determines that they can still benefit from continued treatment, they can receive the study drug free of charge until disease progression, development of intolerable toxicity, the investigator determines it is no longer appropriate for the participant to continue receiving the study drug, or the sponsor terminates the study.

Table 1-1. Clinical Trial Flow Diagram

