Note: Unless otherwise specified, all assessments, examinations, and sample collections should be performed on the same day before drug administration.

Screening Period: Routine examinations or examination results obtained at a tertiary hospital (or this hospital) within 28 days prior to the first dose (unless otherwise specified) and before signing the informed consent form (ICF) can be used for screening, and do not need to be repeated.

Treatment Period (DLT Evaluation Period): For the first intratumoral injection of CNSI-Fe, safety assessments will be performed on Day 7 (± 1 day), Day 14 (± 1 day), and Day 21 (± 1 day) after the first dose to evaluate DLT.

Maintenance Treatment Period: After the DLT evaluation is completed, subjects without unacceptable toxicity will continue to the maintenance treatment period if the investigator determines that the benefit of continued treatment outweighs the risk. During the maintenance treatment period, subjects will receive one more dose of the investigational drug (intratumoral injection to the lesion, tentatively scheduled for Day 1, the dosing regimen may be adjusted based on the PK characteristics of this study by the sponsor and investigator).

Early Termination/End of Treatment (EOT) Visit: This will be scheduled within 7 days after the decision to discontinue treatment. If the assessments required for the

EOT visit were performed within 7 days prior to the EOT visit, they do not need to be repeated.

Safety Follow-up: Subjects who have received at least one dose of the study drug will undergo a safety visit 28 days (± 3 days) after the last dose. If the assessments required for the safety visit were performed within 3 days prior to the safety visit, they do not need to be repeated.

Medical History and Treatment History: Collected during the screening period, including past medical history, medication history (concomitant treatments within 4 weeks prior to screening and currently ongoing), history of all previous tumors (including tumor stage, diagnosis date, genetic test results), history of all previous anti-tumor treatments, family history, surgical history, immunization history, allergy history, smoking history, alcohol history, history of drug abuse/dependence, etc.

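### Ending follow-up and the study 28 days after the last dose leaves no room to confirm a response in one-dose subjects, and too little in some two-dose subjects

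*Combined protocol and SAP*

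**What the plan says.** **End of follow-up.** The Study Period part of the synopsis gives, after treatment, only "Safety follow-up until 28 days after the last dose". The Safety Follow-up note under Table 1-1 says that every treated subject "will undergo a safety visit 28 days (± 3 days) after the last dose". The section headed Research on time uses the same rule for the whole trial: "The study is expected to end 28 days after the last participant receives a maximum of two doses". The available text describes no separate tumor follow-up.

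**Dosing calendar.** The DLT period is a 21-day first cycle. Subjects judged suitable then enter maintenance, where "subjects will continue to receive one more dose of the investigational drug". Others receive one dose only. The regimen is described as tentative, and no latest date is given for the second dose.

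**Tumor assessments.** The tumor assessment schedule in the synopsis, repeated in the notes under Table 1-1, makes the first scan mandatory at 3-4 weeks. Imaging is then due "once every 7-8 weeks for those who enter the maintenance treatment period", with no statement of the day from which that interval runs. Subjects with a CR or PR "in the first assessment will require confirmation at least 4 weeks later".

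**Use of the data.** ORR and DCR of the injected lesions are named as the primary efficacy endpoints, within the secondary endpoints. They are summarized from best lesion response with Clopper-Pearson intervals.

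**The concern.** The last planned contact is set by the safety rule alone, while the scans run on their own calendar, and the two have not been laid side by side. If the last contact comes before the scan that the plan requires, a response seen at week 3-4 stays unconfirmed for administrative reasons. In two-dose subjects the only planned imaging after the second injection may also fall after the subject has left the study.

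At stake is confirmed ORR of the injected lesions. Cohorts hold 3 to 6 evaluable subjects, so one lost confirmation moves a cohort's confirmed ORR by 1/6 = 17 to 1/3 = 33 percentage points. Preliminary efficacy is also among the data the safety review committee considers when it discusses going beyond 90 mg.

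**Working it through.** The plan gives no figure of its own to reproduce. The check is calendar arithmetic in days, with the first dose at t=0.

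**Inputs**

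| Quantity | Value | Source |
|---|---|---|
| First scan, s | 21-28 (3-4 weeks, taken as from the first dose) | Synopsis, tumor assessment schedule |
| Earliest confirmation | s + 28 | Same |
| Maintenance scan interval | 49-56 days, origin unstated | Same |
| Second dose, d | 21 if given directly after the 21-day cycle | Synopsis, Treatment Period |
| Last visit | last dose + 28 ± 3 | Follow-up Period; Safety Follow-up note |

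**Step 1: one-dose subjects.**
- Last visit: 0 + 28 ± 3 = 25-31.
- Earliest confirmation: 21 + 28 = 49 to 28 + 28 = 56.
- Smallest shortfall: 49 − 31 = 18 days. Against the nominal visit it is 49 − 28 = 21 to 56 − 28 = 28 days.
- Imaging at the safety or early-termination visit does not help. Any visit inside follow-up is at t=31 or earlier, so at most 31 − 21 = 10 days after the first scan, against the 28 required.

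**Step 2: two-dose subjects, second dose at t=21.**
- Last visit: 21 + 28 ± 3 = 46-52.
- Confirmation by the latest visit day needs s + 28 ≤ 52, so s ≤ 24. A first scan at t=21 fits the nominal visit, t=22-24 needs the +3-day window, and t=25-28 cannot be confirmed in time.
- The week 7-8 scan counted from the first dose is due at t=49-56. Of these 8 days, 1 falls by the nominal visit and 4 by its latest day.

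**Step 3: later second dose.** Confirmation fits the nominal visit when s + 28 ≤ d + 28, that is, when s ≤ d.

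| Second dose (t) | Last visit (window) | First-scan days of 8 confirmable by nominal visit | By latest visit day |
|---|---|---|---|
| 21 | 49 (46-52) | 1 | 4 |
| 22 | 50 (47-53) | 2 | 5 |
| 24 | 52 (49-55) | 4 | 7 |
| 28 | 56 (53-59) | 8 | 8 |

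The same counts apply to the 8 days of a week 7-8 scan counted from the first dose.

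**Step 4: other origins for the 7-8 weeks.**
- From the second dose: 21 + 49 = 70 to 21 + 56 = 77.
- From the first scan: 21 + 49 = 70 to 28 + 56 = 84.
- Both lie beyond the latest last visit at t=52, by at least 70 − 52 = 18 days.

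**The case against.** **Missing text.** The grid of Table 1-1 is not reproduced in the text available here, and the tumor assessment note beneath it breaks off mid-sentence. A scan at the safety visit therefore cannot be excluded. This stands as a limit on the two-dose case. The ECG and laboratory notes name the safety follow-up visit and the visible part of the tumor note does not, but that is only suggestive. The one-dose case is unaffected (Step 1).

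**Intended reading of the interval.** A scan at 3-4 weeks plus 4 weeks to confirmation gives exactly 7-8 weeks from the first dose, and a second dose at day 21 plus 28 days is week 7. Counting from the first dose is very probably what was meant. A reader might infer from the other readings that no two-dose subject has planned imaging after the second injection. The documents do not support that as a finding; they support only that the origin is unstated.

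**Timing of the second dose.** No latest date is set, and at t=28 or later the two-dose gap closes if the interval runs from the first dose. This stands.

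**Responders are partly provided for.** The confirmation requirement is not cancelled by the end-of-study sentence. Subjects in CR or PR at study end may continue drug, and investigators may add scans for special changes in disease. So it would be too strong to say that a responder can never be re-scanned. But continued drug is at the investigator's judgment and no scan schedule is shown for it, and added scans are optional. The plan requires the confirmation without giving it a visit.

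**Conclusion.** The point holds as a scheduling conflict. It is firm for one-dose subjects with a CR or PR at week 3-4: confirmation falls at least 18 days after the last visit, whichever origin is taken for the 7-8 weeks. For two-dose subjects it holds at the nominal schedule, where first scans at t=25-28 cannot be confirmed by t=52. There it rests on the second dose following directly after the 21-day cycle and on no scan being scheduled in the missing text.

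What can be lost is the second or confirmatory scan, and so confirmed ORR. The efficacy text does not say whether an unconfirmed CR or PR counts as best response, so the effect on reported ORR depends on a rule not visible here.

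Two stronger inferences are not supported. A reader might conclude that some subjects have no tumor measurement at all, but the week 3-4 scan is mandatory for everyone. A reader might also expect distorted DCR, or losses concentrated at higher doses. Neither is shown: disease control can be read from the week 3-4 scan, and a dose pattern would need toxicity-related stopping to rise with dose, for which the documents give no figures. Efficacy here is secondary and descriptive, in up to 30 subjects.

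**What to change.** 1. In the tumor assessment schedule of the synopsis and the matching note under Table 1-1, state that the 7-8 week assessment is counted from the first dose. For a maintenance subject with a first-scan response, the same scan can then serve as confirmation if it is at least 28 days after the first.
2. In Follow-up Period, the Safety Follow-up note and Research on time, separate tumor follow-up from safety follow-up. Each subject's follow-up ends at the later of the safety visit and the outstanding required scan. That scan is the week 7-8 scan for maintenance subjects, or the confirmation scan at least 4 weeks after a first-scan CR or PR, including in subjects who receive only one dose. Study end is the last such date.

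Tying the second scan to the safety visit looks simpler but should be avoided. At the nominal schedule, confirmation on day 28 after the second dose needs the first scan by t=21, which cuts the 3-4 week window to about one day.

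**Cost.** Protocol wording, and no scan beyond those already required. Some subjects stay longer: up to about 1 week for two-dose subjects (56 − 49 = 7 days) and about 3-4 weeks for one-dose responders (49 − 28 = 21 to 56 − 28 = 28 days). Study end may move by the same amount.
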